9.4.4 Reporting to Drug Manufacturer by Sponsor-Investigator

All Suspected Unexpected Serious Adverse Reactions (SUSARs) will be submitted to Mirati Therapeutics on a MedWatch Form 3500A within the timelines as follows:

• Reports of fatal or life threatening Serious Adverse Drug Reactions will be forwarded within five (5) calendar days of Receipt Data

Reports of Serious Adverse Drug Reactions (other than fatal or life threatening) will be forwarded within twelve (12) calendar days of Receipts Date.

Please FAX IND Safety Reports (SUSARS) to [name]. For FAX problems call 1-800-

Please FAX IND Safety Reports (SUSARS) to [name]. For FAX problems call [name] to report the event via phone.

In addition, all reports prepared for FDA submission will be submitted to Mirati Therapeutics prior being submitted to the FDA. If no comment is received by Mirati Therapeutics within 48 hours, the report will be submitted to the FDA in its original form, so as to ensure timely submission of documentation.

9.5 Reporting Process

Adverse events may be submitted on FDA Form 3500A, the HICCC DSMC Serious Adverse Event Reporting Form, or in a narrative format. If supplied as in a narrative format, the minimum information to be supplied is noted above at the beginning of section 10. At the time of IRB renewal or at the request of the manufacturer, the Sponsor-Investigator will submit a summary of all serious adverse events that have occurred during the study to the manufacturer.

10. PHARMACEUTICAL INFORMATION

10.1 Description

MGCD516 is an orally available small molecular inhibitor of several closely related receptor tyrosine kinases. Detailed information on the drug's mechanism of action, as well as preclinical and clinical safety information, is provided in Section 4. The drug is currently supplied as 10 and 40 mg capsules. The composition of the drug product includes a blend of the free base substance MGCD516 with microcrystalline cellulose (Avicel PH302) and polysorbate 80 (Tween 80). The blend is filled into size 1 light blue opaque (10 mg) or size 1 Swedish orange opaque (40 mg) hard gelatin capsules. The 10 and 40 mg capsules are packaged into 60 cc bottles.

10.2 Treatment Regimen

The treatment regimen consists of MGCD516 at a dose of 120 mg orally daily in continuous 21 day cycles. This dose will be administered as three (3) 40 mg capsules. The drug will be administered in the fasted state, at least 2 hours after the previous meal, and 1 hour before the next meal. The capsules will be taken in the morning hours (1 hour before breakfast or 1 hour before lunch). The study capsules will be taken with at least 200 mL (1 cup) of water.

10.3 Method for Assigning Subjects to Treatment Groups

Not applicable. All study participants will be treated with the same treatment regimen.

10.4 Preparation and Administration of Study Drug

The study drug is an oral capsule which will be packaged, shipped and stored as described below. The drug will be received by the Research Pharmacy of Columbia University Medical Center, stored in a secure location and according to all institutional policies, and will be released to the research nursing staff who will distribute the agent to the patient. No other specific preparation of the drug is needed at the study site.

10.5 Subject Compliance Monitoring

Study subjects will complete a medication journal documenting compliance with the study drug. The medication journal will be reviewed after each cycle. Patients who are non-complaint with the treatment regimen may be removed from the study at the discretion of the principal investigator.

10.6 Prior and Concomitant Therapy

Information will be collected on all prior anti-cancer therapies. Patients may not receive any other agent which could be considered treatment for the primary neoplasm or which might affect the primary endpoint during their participation in the study. For other restrictions on concomitant medication use, see section 7.2.

10.7 Packaging

The MGCD516 drug product is packaged in 30 count, high-density polyethylene (HDPE) white opaque round bottles. The 10 and 40 mg unit dose capsules are packaged into 60 cc bottles. A tamper-proof heat induction seal and a child resistant closure are employed. Each bottle is labeled with contents, product lot number, required storage conditions and a regional specific cautionary statement.

10.8 Blinding of Study Drug

Not applicable. This is an open-label study.

10.9 Receiving, Storage, Dispensing and Return

10.9.1 Receipt of Drug Supplies

The study drug will be shipped by Mirati Therapeutics to the Research Pharmacy of Columbia University Medical Center. Upon receipt of the of the study treatment supplies, an inventory will be performed and a drug receipt log filled out and signed by the person accepting the shipment. The designated study staff will count and verify that the shipment contains all the items noted in the shipment inventory. Any damaged or unusable study drug in a given shipment will be documented. The investigator must notify the agent manufacturer of any damaged or unusable study treatments that were supplied to the investigator's site.

10.9.2 Storage

Bottles of MGCD516 will be stored at room temperature, within a range of 15 to 30 degrees Celsius. The storage area should be secure with limited access. Only qualified personnel who are familiar with procedures that minimize undue exposure to them and to the environment should undertake the preparation, handling and safe disposal of small molecule chemotherapeutic agents such as MGCD516.

10.9.3 Dispensing of Study Drug

Regular study drug reconciliation will be performed to document drug assigned, drug consumed, and drug remaining. This reconciliation will be logged on the drug reconciliation form and signed and dated by the study team. Drug inventory forms will record the batch or lot numbers for disposition on a patient by patient basis and signed by the person dispensing the drug. Patients will receive study drug on the first day of each cycle while they remain on study. Sufficient supply will be provided for the cycle and up to 2 additional days in case of delayed clinic visits or lost capsules. Study site personnel will provide each patient with written dosing information. Patients will record their daily dosing on a provided form and report any missed doses or lost capsules.

10.9.4 Return or Destruction of Study Drug

At the completion of the study, there will be a final reconciliation of drug shipped, drug consumed, and drug remaining. This reconciliation will be logged on the drug reconciliation form, signed and dated. Any discrepancies noted will be investigated, resolved, and documented prior to return or destruction of the study drug.

11. STUDY CALENDAR

	Screening (1)	Cycle 1(9)		Cycle 2 (9)		Cycle 3 + (9)			End of study (8)		
		1	8	15	1	8	15	1	8	15	
Procedure											
Informed consent	X										
Medical history	X										
Pathology confirmation	X										
Physical examination and vital signs	X	X	X	X	X			X			X
Height and weight	X	X	X	X	X			X			X
ECOG performance status	X	X	X	X	X			X			X
Adverse event assessment	X	X	X	X	X			X			X
ECG (1)	X										X
Echocardiogram (1)	X							X			
CBC w/differential (1,3)	X	X	X	X	X			X			X
Comprehensive metabolic panel (1,3,4)	X	X	X	X	X			X			X
Thyroid function tests (1, 3, 11)	X							X			X
Lipase (1, 3, 11)	X							X			X
Serum or urine pregnancy test (1)	X										
Urinalysis (1)	X							X (10)			X
CT or MRI of chest, abdomen, pelvis (2)	X							X			X
Tumor specimen submitted for next generation sequencing (5)	X										
Fresh tumor biopsy for RPPA studies (6)	X			X							
Follow-up telephone contact (7)											X

- (1): History and physical, all laboratory studies, urinalysis and single EKG must be completed 14 days or less prior to registration, with the exception of the serum or urine pregnancy test, which must be performed 7 days or less prior to registration. The echocardiogram must be completed within 56 days of registration, unless there is clinical suspicion for a change in cardiac status since that time, in which case it should be repeated. An echocardiogram will be repeated at any point during week 1 of cycle 3. Protocol-specific screening procedures that are performed as part of standard of care and are within these specified timeframes may be used for screening purposes.
- (2) Baseline imaging can include either (a) CT, spiral CT or MRI, or (b) FDG-PET with diagnostic CT performed with IV and oral contrast and CT acquired with 5 mm or less slice thickness. Imaging studies used for baseline tumor measurements must be obtained 28 days or less prior to registration. Imaging studies performed as part of standard care and within this

timeframe may be used for screening purposes. Imaging studies are performed every 2 cycles (6 weeks, 42 days) for the first 36 weeks of study treatment, and then every 3 cycles (9 weeks, 63 days) thereafter. Imaging studies may be performed +/- 5 days from the required date. In the event of dose delays/holds, imaging studies should still be obtained at the scheduled timepoints as determined from registration, without delays to account for the dose delays/holds. Confirmatory scans must be obtained at least 4 weeks after the documentation of an objective response as discussed in section 12. It is acceptable to perform confirmatory assessments at the next appointed evaluation per protocol. Response assessment should include assessment of all sites of disease and use the same imaging method as used at baseline whenever possible.

- (3) All laboratory studies may be performed +/- 3 days from the required date.
- (4) Comprehensive metabolic panel is to include albumin, alkaline phosphatase, total bilirubin, bicarbonate, blood urea nitrogen, calcium, chloride, creatinine, glucose, potassium, total protein, AST, ALT and sodium.
- (5) Applies to liposarcoma patients only: All patients will have their most recent available biopsy material submitted for next generation sequencing to assess for genetic alterations of MGCD516 targets. See section 13 for more information on sample collection, processing and analysis. In cases were institutional policy or availability of prior specimens preclude this analysis, these studies will not be performed for that patient.
- (6) Applies to liposarcoma patients only: A subset of 10 patients will undergo baseline and ontreatment tumor biopsies for RPPA studies. The first 10 patients with lesions amenable to biopsy who are enrolled to the study (beginning with the first patient enrolled in stage I) will undergo these biopsies. See section 13 for information on sample collection, processing and analysis. The baseline biopsy specimen will be obtained at any point between day -14 and the date of first treatment with the study drug (cycle 1, day 1) provided consent is obtained and the other eligibility criteria are met. The on-treatment biopsy specimen will be performed with a target timepoint of cycle 1 day 15 (with a window of cycle 1 days 15 through 20). Biopsies will be obtained from the site of disease. If the study fails in stage I and proceeds to the exploratory cohort, no further RPPA analyses will be performed.
- (7) A post-study follow-up contact via telephone by research staff will be conducted every 3 months during the first year after the end of study participation, and then every 6 months thereafter. For patients who do not progress on study treatment, information is obtained on disease status, survival status, and new anti-cancer therapy received. For patients who do progress on treatment, information is obtained on survival status and new anti-cancer therapy received. Follow-up continues for at least 3 years as measured from the date of study registration or until death, whichever comes first.
- (8) The end-of-study visit must be scheduled 28 days after the last dose of study drug (+/- 7 days) and before starting any new anti-neoplastic therapy. Imaging studies are only performed at this time if they would otherwise be indicated by that patient's study calendar.
- (9) Clinical assessments will occur on days 1, 8 and 15 of cycle 1, and then on day 1 of all cycles

thereafter. Clinical assessments may occur +/- 3 days from the target date.

- (10) The urinalysis is repeated on cycle 3 day 1. If there is no evidence of proteinuria, the urinalysis need not be repeated in subsequent cycles. If microscopic testing shows evidence of proteinuria, the study should be repeated on day 1 of subsequent studies.
- (11) Thyroid function tests (TSH, reflexive free T4/free T3 if TSH is abnormal) and lipase should be performed at baseline, C3D1, every other cycle after C3D1 (i.e. C5D1, C7D1 etc.) and at end of treatment.

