Single dose pharmacokinetic parameters were evaluated in 24 patients, and steady state parameters in 20 patients. Plasma samples for pharmacokinetic analyses were collected over a 168-hour period following single dose administration and a 24-hour period following repeat dose administration. Drug concentrations were determined using a validated LC MS/MS method. After single administration, the drug reached peak concentration over a median time of 3 to 9 hours. Plasma exposure levels were found to increase in a dose proportional fashion. Mean elimination half-life varied between 40 and 53 hours. Steady state pharmacokinetics were reached in 11-15 days. Drug accumulation was observed following multiple dosing, averaging 4.2-fold for C_{max} and 4.7-fold for AUC₀₋₂₄. Mean value for peak to trough fluctuation was 53.8%. At the 100 mg dose level, mean steady state C_{avg} was 123 ng/mL, C_{max} was 151 ng/mL and AUC was 2590 ng*h/mL.

On 2/6/2018, Mirati Therapeutics provided updated guidance to investigators participating on the industry sponsored phase 1/1b study of Sitravatinib in solid tumors. In this study, Sitravatinib appeared to have improved long-term tolerability at a dose of 120 mg based on assessment of toxicities observed in patients starting at this dose, and in patients dose reduced from 150 to 120 mg. Furthermore, analysis of pharmacokinetic data suggest plasma concentrations for Sitravatinib are comparable at the 120 and 150 mg dose levels. Therefore, the recommended starting dose of Sitravatinib for the phase 1/1b study was modified to 120 mg, which has also been adopted in this study effective in 5/2018. Patients already enrolled on this study may continue at the 150 mg dose level, or reduce the 120 mg level, as determined by the treating investigator.

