7.2.4 Medications affecting the qTC interval

The risk for qTC prolongation in patients receiving treatment with MGCD516 has not been adequately characterized in humans. Therefore, use of medications known to prolong the QTc interval and pose a risk of Torsades are prohibited during treatment with MGCD516. The use of medications known to prolong the QTc and pose a conditional risk of Torsades should be used with caution. Please see Appendix 1 for a list of medications to be avoided and used with caution in this setting.

7.3 **Duration of Therapy**

Treatment with the study drug will continue until one of the following applies:

- Disease progression
- Intercurrent illness that prevents further administration of treatment
- Unacceptable adverse event
- Patient's decision to withdraw from the study
- General or specific changes in the patient's condition render the patient unacceptable for further treatment in the judgment of the investigator

Patients whose disease status remains complete response, partial response or stable disease may

continue on therapy indefinitely until one of the above conditions applies.

7.4 **Duration of Follow Up**

Patients who do not progress while on study treatment will be followed every 3 months after completion of study treatment for the first 12 months of follow up and then every 6 months for both survival and disease status until death or for a period of at least 3 years, whichever comes first. For patients who are taken off therapy due to progression, information on survival will also be collected every 3 months after completion of study treatment for the first 12 months of follow up and then every 6 months until death or for a period of at least 3 years, whichever comes first. Patients removed from study for unacceptable adverse events will also be followed for information on resolution or stabilization of the adverse event.

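### No ECG is scheduled while patients are on drug: the only one after baseline comes 21 to 35 days after the last dose, although the protocol regards the QTc risk as not adequately characterized

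*Combined protocol and SAP*

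**What the plan says.** Section 7.2.4 states: "The risk for qTC prolongation in patients receiving treatment with MGCD516 has not been adequately characterized in humans". On that ground it prohibits drugs known to prolong QTc with a risk of Torsades and allows conditional-risk drugs with caution. Exclusion 5.2.2(c) keeps out patients who need the prohibited drugs, and Appendix 20.1.5 lists them.

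The ECG row of the study calendar (section 11) has two marks, screening and end of study. The nine columns for days 1, 8 and 15 of cycles 1, 2 and 3+ are empty. Note 1 covers only the screening recording: "single EKG must be completed 14 days or less prior to registration". Note 8 times the other one: "The end-of-study visit must be scheduled 28 days after the last dose of study drug (+/- 7 days". No other section schedules an ECG in patients, and the dose-modification tables in section 8 have no QTc entry.

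Section 3.2 gives the human pharmacokinetics: "Mean elimination half-life varied between 40 and 53 hours"; "Steady state pharmacokinetics were reached in 11-15 days"; and "Drug accumulation was observed following multiple dosing, averaging 4.2-fold" for Cmax, with 4.7-fold for AUC over 24 hours.

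**The concern.** The protocol names a cardiac uncertainty and then times its two planned ECGs so that one precedes the drug and the other follows its elimination. A QTc effect that depends on concentration and reverses on stopping would be absent from both, whatever its size in treated patients. Treatment can continue indefinitely without progression or toxicity (section 7.3), so a patient could be exposed for many months with no scheduled recording on drug.

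The other safety tests do not share this gap. Blood counts, chemistry, thyroid function, lipase, urinalysis and the echocardiogram all have on-treatment marks. The echocardiogram does not measure QTc.

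What is at stake is the safety description (secondary objective 2.2.1). A reader who saw ECGs before and after treatment, both normal, could take them as reassurance that they cannot give.

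**Working it through.** **1. Is the calendar row read correctly?** The table was extracted from PDF, so the column positions need a check. Counted the same way, the repeat echocardiogram falls on cycle 3 day 1, which agrees with note 1: "An echocardiogram will be repeated at any point during week 1 of cycle 3". The on-treatment biopsy falls on cycle 1 day 15, which agrees with note 6. The ECG marks in the first and last columns are therefore not an extraction artefact.

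**2. Do the plan's own pharmacokinetic figures agree with each other?**
- Steady state: the fraction reached after time t is 1 − 2^(−t/t½). At 11 days (264 h) and t½ = 53 h it is 96.8%. At 15 days (360 h) and t½ = 40 h it is 99.8%. The stated 11 to 15 days fits the stated half-life.
- Accumulation: with dosing every 24 h, R = 1/(1 − 2^(−24/t½)). This gives 2.9 at 40 h and 3.7 at 53 h, below the reported 4.2 and 4.7. Solving for R = 4.7 gives t½ = 24 × ln 2 / −ln(1 − 1/4.7) = 69.5 h. I use this as a conservative sensitivity value.

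**3. How much drug is left at the end-of-study ECG?** The visit is at 28 ± 7 days, so 504, 672 or 840 h after the last dose. Half-lives elapsed = hours / t½; fraction remaining = 2^(−half-lives).

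| Day after last dose | t½ = 40 h | t½ = 53 h | t½ = 69.5 h (implied by 4.7-fold) |
|---|---|---|---|
| 21 | 12.6 half-lives, 0.016% | 9.5, 0.14% | 7.3, 0.66% |
| 28 | 16.8, 0.0009% | 12.7, 0.015% | 9.7, 0.12% |
| 35 | 21.0, 0.00005% | 15.8, 0.0017% | 12.1, 0.023% |

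For an individual with an assumed half-life of 100 h, which is not a figure from the documents, 3.0% would remain at day 21 (5.04 half-lives) and 0.9% at day 28 (6.72).

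**4. Do existing visits fall at steady state?** Clinic visits are already planned on cycle 1 day 15 and on day 1 of every later cycle. After 14 full days of uninterrupted dosing (336 h), 98.8% of steady state is reached at t½ = 53 h and 96.5% at 69.5 h. After 21 days (504 h) the figures are 99.9% and 99.3%.

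**The case against.** The strongest reply is that the trial never set out to measure QTc. Objective 2.2.1 assesses safety through adverse event rates, section 15.4 reports counts and percentages by grade, and no planned analysis uses ECG data. The protocol answers its uncertainty by avoiding risk, through exclusion 5.2.2(c), section 7.2.4 and Appendix 20.1.5, together with a screening ECG. How intensively to monitor beyond that is partly a matter of judgement.

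The background evidence is also mild. The telemetry study in dogs (section 3.1.6) found no qualitative ECG abnormality. PR and QT lengthened slightly and heart rate fell at the top dose, but QTc did not change. The four-week dog study (section 3.1.5) found no effect on electrocardiograms. QT prolongation is not in the summary list of treatment-related events from 61 phase 1/1b patients (section 9.1), although the documents do not say how ECGs were monitored there.

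All of this stands, and it limits the point. A reader might infer that the trial cannot detect any QTc effect, or that marked prolongation would come to light only through symptoms. The documents do not support either. Section 9.3 requires questioning at every contact and examination where appropriate, and section 9.2 makes clinically significant abnormal test results adverse events. An ECG prompted by clinical judgement would be captured. The limitation applies to the scheduled ECGs.

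The objection does not supply a scheduled on-drug reading. Restricting co-medication reduces added risk but gives no information about the drug itself, and questioning does not reveal prolongation without symptoms.

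**Conclusion.** The point holds in a limited form. The plan schedules no ECG on treatment in any patient. The only post-baseline ECG is taken when at most about 0.14% of the drug remains at the stated mean half-lives, or about 0.7% at the longer half-life implied by the accumulation data. It cannot show a reversible drug effect on QTc, while section 7.2.4 regards that effect as not adequately characterized in humans.

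The result rests on first-order elimination and on mean phase 1 half-lives. It is not sensitive to either half-life used, and even the assumed 100 h leaves only 3.0% at the earliest permitted visit. It would not apply to an effect that outlasts exposure, which a post-washout ECG could show.

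This does not affect the 12-week progression-free rate or the two-stage decision, and no stated endpoint is broken. A reader might also infer that an on-drug ECG would settle the QTc question. It would not: one unreplicated recording per patient, uncontrolled, in about 29 patients can flag marked individual prolongation but cannot characterize QTc.

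**What to change.** Reconcile section 7.2.4 with the ECG row and note 8 of section 11. Retime the post-baseline ECG that is already planned to an existing clinic visit while the patient is on drug at steady state. Record the time since the last dose with it, and report change in QTc from screening descriptively. The choice among existing visits is the sponsor's, and no rule for acting on the result is proposed here.

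The number of ECGs and visits per patient does not change. The costs are:
- no routine post-washout ECG at the end-of-study visit;
- no post-baseline ECG for a patient who stops before the chosen visit;
- a calendar amendment, which section 19.2 requires the affiliate sites' local IRBs to approve.

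If the calendar is left as it is, the report should state that no on-drug ECG was scheduled and should draw no QTc conclusion from the two planned recordings.

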7. TREATMENT PLAN

7.1 Agent Administration

Treatment will be administered on an outpatient basis. Reported adverse events and potential risks for MGCD516 are described in Section 10. Appropriate dose modifications for MGCD516 are described in Section 9. No investigational or commercial agents or therapies other than those described below may be administered with the intent to treat the patient's malignancy.

REGIMEN DESCRIPTION					
Agent	Premedications; Precautions	Dose	Route	Schedule	Cycle Length
MGCD516	None	120 mg	Orally	Daily	21 days

The patient will be requested to maintain a medication diary of each dose of medication. The medication diary will be returned to clinic staff at the end of each cycle of treatment.

The drug will be administered in the fasted state, at least 2 hours after the previous meal, and 1 hour before the next meal. The capsules will be taken in the morning hours (1 hour before breakfast or 1 hour before lunch). The study capsules will be taken with at least 200 mL (1 cup) of water. No predefined prophylactic or supportive care medications will be administered with the study agent for patients newly starting therapy. However, prophylactic or supportive care may be initiated in the event of toxicity as described in section 9.

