8.2 Management Advice for Non-Hematologic Adverse Events

Hypertension	Management/Next Dose for MGCD516
≤ Grade 1	No change in dose

Hypertension	Management/Next Dose for MGCD516		
Grade 2	Continue therapy. Institute anti-hypertensive agent or alter dose of		
Grade 2	existing anti-hypertensive agent.		
	Hold therapy. Institute anti-hypertensive agent or alter dose of		
	existing agent. Resume therapy when hypertension resolved to grade		
Grade 3	2 or less. For subsequent occurrences at grade 3, hold therapy until		
	blood pressure resolves to grade 2 or lower, and reinstitute at one		
	dose level lower, at investigator's discretion.		
Grade 4	Off protocol therapy.		

When anti-hypertensive therapy is indicated, the agent employed should be based upon review of the patient's clinical history to determine the most appropriate agent, with cardiology consultation as needed. The use of dihydropyridine calcium channel blockers such as nifedipine, amlodipine and nicardipine can be considered as first line agents, in the absence of contraindications.

Palmar Plantar Erythrodysesthesia	Management/Next Dose for MGCD516	
≤ Grade 1	No change in dose. Counsel on measures to mitigate the effects of palmar plantar erythrodysesthesia and institute topical therapies as described below.	
Grade 2	Hold until ≤ Grade 1, counsel on measures to mitigate the effects of palmar plantar erythrodysesthesia, and resume at one dose level lower.	
Grade 3	Hold until ≤ Grade 1, counsel on measures to mitigate the effects of palmar plantar erythrodysesthesia, and resume at one dose level lower, at investigator's discretion.	
Grade 4	Not applicable.	

Signs and symptoms of palmar plantar erythrodysesthesia include redness, swelling, pain and blistering on the palms of the hands and soles of the feet. Patients should be counseled to avoid exposure of hands and feet to hot water and other sources of heat, to avoid activities causing force or friction, and to avoid contact with harsh chemicals. Treatment includes the use of moisturizing agents, topical anesthetics, topical anti-inflammatory medications, and topical corticosteroids.

Proteinuria	Management/Next Dose for MGCD516
≤ Grade 1	Continue therapy with close monitoring by urinalysis at least every cycle.

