Grade 2	Hold protocol therapy. Perform 24 hour urine collection to confirm degree of proteinuria. May reinstitute at one dose level lower if and when protein levels decrease to 2g in 24 hours, at the discretion of the principal investigator.
Grade 3	Off protocol therapy.
Grade 4	Not applicable.

Patients who develop more than 2g proteinuria should undergo 24 hour urine collection for definitive assessment of urine protein. Patients who develop nephrotic syndrome should be

Proteinuria	Management/Next Dose for MGCD516	
taken off protocol therapy and referred for further management by a nephrologist. ACE		
inhibitor therapy is permitted in study patients as clinically indicated.		

Diarrhea	Management/Next Dose for MGCD516
< Grade 1	No change in dose. Evaluate for infectious etiology if clinically
≥ Grade 1	indicated. Institute anti-diarrheal therapy.
	No change in dose. Evaluate for infectious etiology if clinically
	indicated. Institute anti-diarrheal therapy. If diarrhea persists at grade 2
Grade 2	or higher for more than 5 days despite supportive care, hold protocol
Grade 2	therapy and manage supportively. Reinstitute at same dose when
	symptoms improve to \leq grade 1. On subsequent occurrences at grade 2,
	consider dose reduction when therapy reinstated.
	Hold until ≤ Grade 1. Evaluate for infectious etiology if clinically
Grade 3	indicated. Institute anti-diarrheal therapy. Reinstitute at one dose level
	lower when symptoms improve to \leq grade 1.
Grade 4	Off protocol therapy.

If clinically indicated, evaluate patients for an infectious etiology of diarrhea using appropriate test for Clostridium difficile, stool cultures, and PCR for GI pathogens, where available. Treat infection as clinically indicated. First line supportive care should be instituted with the anti-diarrheal loperamide.

Fatigue	Management/Next Dose for MGCD516	
≤ Grade 1	No change in dose.	
Grade 2	No change in dose.	
Grade 3	Hold until \leq Grade 2. Resume at same dose level. If recurs at grade 3, hold until \leq Grade 2 and then resume at one dose level lower.	
Grade 4	Not applicable.	

Fatigue is commonly associated with receptor tyrosine kinase inhibitors. Evaluate and treat for other conditions which can manifest as fatigue, including but not limited to thyroid dysfunction, infection and anemia.

Left ventricular systolic dysfunction	Management/Next Dose for MGCD516
≤ Grade 1	Not applicable.
Grade 2	Not applicable.
Grade 3	Off protocol therapy.

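### After a negative cycle 3 day 1 urinalysis, no further on-treatment urine test is scheduled, so silent proteinuria that starts later has no planned trigger for the hold and removal rules (minor safety point, cheap to fix)

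*Combined protocol and SAP*

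**What the plan says.** **Calendar.** The urinalysis row in section 11 is marked at screening, on day 1 under cycle 3 and later (qualified by note 10), and at end of study. Cycles 1 and 2 are not marked.

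**Note 10.** The test is repeated on C3D1. If that result is negative: "If there is no evidence of proteinuria, the urinalysis need not be repeated in subsequent cycles". If it is positive: "If microscopic testing shows evidence of proteinuria, the study should be repeated on day 1 of subsequent studies". The note does not mention a positive result at screening.

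**Note 8.** The end-of-study visit is 28 days after the last dose, with a window of 7 days either way.

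**Note 11.** Thyroid tests and lipase "should be performed at baseline, C3D1, every other cycle after C3D1 (i.e. C5D1, C7D1 etc.) and at end of treatment".

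**Section 8.2, proteinuria table.** The row labelled ≤ Grade 1 reads "Continue therapy with close monitoring by urinalysis at least every cycle". Grade 2 reads "Hold protocol therapy. Perform 24 hour urine collection to confirm degree of proteinuria", with a possible restart one dose level lower. Grade 3 takes the patient off protocol therapy.

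**Other places.** Section 7.3 sets no upper limit on treatment for patients without progression. The organ-function list in 5.1.8 sets no urine-protein limit. Section 9.1 lists urine protein in its under-3% column, based on 61 patients.

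**The concern.** Both action rules in the proteinuria table need a urine result. After a negative test on study day 43, the calendar asks for no other until dosing has already stopped. A site that follows the schedule exactly could therefore keep dosing a patient whom 8.2 would hold or remove. Testing after the last dose comes too late for either rule to protect that patient.

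The second issue is a mismatch. A patient with proteinuria at screening can enroll, and the calendar then schedules nothing until day 43, while the first row of the 8.2 table calls for urinalysis every cycle. Two parts of the protocol give the site different schedules for the same patient.

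What is at stake is the safety of individual patients. The 12-week progression-free rate and the two-stage decision rule do not depend on urinalysis.

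**Working it through.** The plan states no figure on this point, so there is none to reproduce. The check is calendar arithmetic plus a rough size.

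**Inputs from the protocol.** 21-day cycles (7.1); end-of-study visit at last dose + 28 ± 7 days (section 11, note 8); 29 patients in total on either route (15.1); 12-week progression-free rate p between 0.20 and 0.40, the two design values (15.1); urine protein in the under-3% column, 61 patients (9.1).

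**Assumptions.** Constant hazard of progression or death, treatment until that event, and the same p for all 29 patients.

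**1. Gap after a negative C3D1.** Day 1 of cycle n is 21(n − 1) + 1, so C3D1 is day 43. For chosen last-dose days:

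| Last dose (day) | Days on drug after C3D1 | Days from C3D1 to end-of-study test (window) | Day 1 visits without urinalysis | On-drug tests if done every other cycle from C5D1 |
|---|---|---|---|---|
| 84 | 41 | 69 (62–76) | 1 | 0 |
| 126 | 83 | 111 (104–118) | 3 | 1 |
| 252 | 209 | 237 (230–244) | 9 | 4 |
| 365 | 322 | 350 (343–357) | 15 | 7 |

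The last column counts C5D1 = day 85, C7D1 = 127, C9D1 = 169 and so on, up to C17D1 = 337.

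**2. How many patients this concerns.** On drug at 6 weeks: 29 × p^0.5 = 29 × 0.447 = 13.0 at p = 0.20, and 29 × 0.632 = 18.3 at p = 0.40.

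**3. How long they go untested.** Mean weeks on drug after C3D1: 12/(−ln p) = 7.5 to 13.1. Adding 4 weeks to the end-of-study visit gives 11.5 to 17.1 weeks. Adding 3 weeks at the low end and 5 at the high end, for the ± 7 day window, gives 10.5 to 18.1. A 12-month patient has 322/7 = 46 weeks on drug without a scheduled test, but the number expected to last 52 weeks is only 29 × p^(52/12) = 0.03 to 0.55.

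**4. Expected cases.** Two of 61 is 3.3%, which is not under 3%. A listed event in that column is therefore taken as 1 of 61 (1.6%).

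- Cases among those reaching C3D1: 12.97/61 = 0.21 to 18.34/61 = 0.30.
- Chance of at least one: 1 − (60/61)^12.97 = 19% to 1 − (60/61)^18.34 = 26%.

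At that rate these figures overstate the problem, because they include onset before C3D1 and grade 1, which needs no hold.

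**5. Added tests under every-other-cycle urinalysis.** Per patient reaching C3D1: r/(1 − r) with r = p^0.5, giving 0.81 to 1.72. In the whole trial: 12.97 × 0.81 = 10.5 to 18.34 × 1.72 = 31.6.

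**The case against.** **A deliberate, risk-adapted schedule.** Note 10 tests after six weeks on drug and continues only if needed, for a rare event. It permits extra tests. Every day 1 visit still includes adverse-event questioning, examination, vital signs, weight, and serum albumin, total protein and creatinine, and the safety committee reviews toxicity. All of this is true and keeps the point minor. None of these checks measures urine protein, however, so they are weak triggers for symptom-free proteinuria.

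**The lipase comparison.** It shows only that another test has another frequency; no document fixes a required urinalysis interval. That stands. The comparison does show that repeat testing at this interval is already accepted for an event in the same under-3% column, one with no table of its own in 8.2.

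**Screening-positive patients.** A reader might infer that they go untested in cycles 1 and 2. The documents do not support that. The ≤ Grade 1 row of 8.2 on its face reaches them. Section 8 is framed around adverse events, and 9.2 treats a finding at entry as a baseline condition, but 8.2 also deals with baseline abnormality elsewhere (the bilirubin note in the liver table). The sound finding is a mismatch between calendar and 8.2.

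**A flat contradiction for everyone.** A reader might also take ≤ Grade 1 to include grade 0, so that 8.2 requires testing every cycle in all patients and contradicts note 10. The label is ambiguous. In the hand-foot table the same label says to "institute topical therapies as described below", which presupposes an event, since 7.1 states "No predefined prophylactic or supportive care medications will be administered with the study agent for patients newly starting therapy". In the hypertension and fatigue tables it fits grade 0 without difficulty. The text does not settle the matter.

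**Conclusion.** The point holds as a minor safety improvement. After a negative C3D1, no urine test is scheduled until about 28 days after the last dose, although treatment has no fixed end. The calendar and 8.2 also differ for patients positive at screening.

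Fewer than one case is expected: 0.21 to 0.30, or a 19% to 26% chance of at least one, counting early onset and grade 1. A reader might multiply 18.34 patients by the 3% column limit and report 0.55 cases and a 43% chance; 61 patients cannot yield an observed rate under 3% with more than one case, so those figures should not be used.

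The size rests on the constant-hazard assumption and on reading the listing as 1 of 61. Stopping for toxicity or withdrawal would shorten exposure and lower it. The documents do not say how often urine was tested in those 61 patients, so the true rate of silent proteinuria is uncertain. The gap itself follows from the calendar and needs no assumption.

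**What to change.** Amend the urinalysis row and note 10:

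- After a negative C3D1, dipstick urinalysis every other cycle (C5D1, C7D1 and so on), on the schedule note 11 already uses.
- After any positive result, including at screening, urinalysis on day 1 of every cycle.
- In note 10, replace *microscopic testing* with *urinalysis*, and *subsequent studies* with *subsequent cycles*.

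Leave the ≤ Grade 1 row of 8.2 as it is, or add a cross-reference to note 10. Narrowing it to grade 1 would remove the only text that can be read as requiring every-cycle testing in all patients.

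**Cost.** A wording amendment and about 10 to 32 added urine tests in the whole trial for patients negative at screening and C3D1. For such a patient that means none in the first 12 weeks and 7 over 12 months. A screening-positive patient has up to 3 added tests in the first 12 weeks (C1, C2, and C4 if C3D1 is negative). All fall at day 1 visits that already take place. The longest scheduled on-drug gap after C3D1 becomes 6 weeks, against 46 for a 12-month patient now.
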